### 6.3 Reporting

#### 6.3.1 Adverse Event

Adverse Events will be collected by the Investigator or qualified designee(s) from the time a subject signs the Informed Consent Form through the follow-up phone calls (Day 11+1 day). Any AE (serious or non-serious) observed by the Investigator (or a

Protocol Pa-824-CL-011 V1.0

suitably medically qualified designee) or reported by the subject will be recorded on the Adverse Event Case Report Form. The Investigator will review each AE and assess its relationship to drug treatment based on all available information at the time of the completion of the CRF. The following information will be recorded for each Adverse Event reported:

- Diagnosis of the AE, if possible. In the case where an overall diagnosis cannot be made, each specific sign and/or symptom will be recorded as individual AEs;
- Date of onset;
- Stop date (with duration, if applicable);
- Severity;
- Action taken with IMP;
- Other action taken;
- Outcome;
- Relationship to IMP;
- Occurrence;
- Seriousness

#### **6.4 Serious Adverse Event Reporting**

The Investigator or designee will notify the appropriate Sponsor contact immediately after the SAE detection, observation, or report of occurrence (regardless of the relationship to test article). The Sponsor contact information for SAE reporting is provided below:

PPD PVG (pharmacovigilance service provider for TB Alliance)

Email: [[contact]](mailto:[contact])

Safety [contact]

Safety [contact]

And

[name], MD

Global Alliance for TB Drug Development

[name]

[name], United States of America

[contact]

[contact]

[contact]

Email: [[name]](mailto:[name])

These SAE reports must contain the following information:

- A. Study name/number (for EU also the EudraCT number)

Protocol Pa-824-CL-011 V1.0

- B. Study drug
- C. Investigator details (name, phone, fax, e-mail)
- D. Subject number
- E. Subject demographics
- F. Clinical event:
  - 1) Description
  - 2) Date of onset
  - 3) Treatment (drug, dose, dosage form)
  - 4) Adverse event relationship to study drug
  - 5) Action taken regarding study drug in direct relationship to the AE
- G. If the AE was fatal or life-threatening
- H. If applicable, cause of death (whether or not the death was related to study drug)
- I. If applicable, autopsy findings (if available)

Any new SAE that occurs within one month after the study period and is considered to be possibly related to the Investigational Product (IP) should be recorded and reported immediately to the Sponsor.

The person responsible for the study shall take care that the study has been carried out in accordance with pharmacovigilance local regulations.

All serious event reporting will adhere to U.S. Code of Federal Regulations (21 CFR Part 312.32) for IND drugs and 21 CFR 314.80 for marketed drugs (15-day alerts). The Institutional Review Board (IRB) will be notified of the alert reports per Food and Drug Administration (FDA) regulations.

All AEs, including SAEs, will be followed to resolution when possible. All AEs and treatment administered will be recorded on the case report form (CRF).

The Sponsor will be responsible for processing and reporting any SAEs (and their relevant updates) to the FDA or other applicable regulatory agency.

## 6.5 Follow up of Adverse Events

All AEs will be followed until:

- Satisfactory clinical resolution or stabilization; or
- End of the follow-up period; and
- All queries on these AEs have been resolved.

Certain long-term AEs cannot be followed until resolution within the setting of this protocol. In these cases, follow-up will be the responsibility of the treating physician. However, this will have to be agreed upon with the Sponsor Medical Monitor.

The investigator is obligated to perform or arrange for the conduct of supplemental measurements and/or evaluations as medically indicated or as requested by Sponsor or representative to elucidate the nature and/or causality of the AE or SAE as fully as possible. This may include additional laboratory tests or investigations, histopathological examinations, or consultation with other health care professionals. Investigator should contact sponsor/designee to discuss appropriate medical follow-up if consultation required.

If a participant dies during participation in the trial or during a recognized follow-up period, the investigator will provide sponsor/representative with a copy of any post-mortem findings including histopathology.

New or updated information on an SAE will be recorded in the originally completed CRF and submitted to sponsor within 24 hours of the information becoming known per SAE reporting guidelines.

## **6.6 Post-Trial Serious Adverse Events**

Any new SAEs reported by the subject to the Investigator that occur up to 30 days after last contact and are determined by the Principal Investigator to be possible, probable or very likely related to the use of the IMP, will be reported to the Sponsor, IRB and FDA on an expedited basis as required in accordance with local requirements and ICH guidelines for GCP.

## **6.7 Clinical Laboratory Adverse Events**

Changes in the results of the Clinical Laboratory assessment results which the Investigator feels are clinically significant will be reported as adverse events. It is the Investigators' responsibility to review the results of all laboratory tests as they become available. This review must be documented by the Investigators' dated signature on the laboratory report. For each abnormal laboratory test result, the Investigator needs to ascertain and document if this is a clinically significant change from baseline for that individual participant. This determination, however, does not necessarily need to be made the first time an abnormal value is observed. The Investigator may repeat the laboratory test or request additional tests to verify the results of the original laboratory tests. If this laboratory value is determined by the Investigator to be a clinically significant change from baseline for that participant, it is considered to be an adverse event.

## **6.8 Drug Interaction**

If the Investigator becomes aware that the subject has experienced a drug interaction which has resulted in an adverse event, it will be recorded as an adverse event.

## **6.9 Pregnancy**

The Investigator will immediately notify the Sponsor of any pregnancy that is discovered during the clinical trial. Pregnancy forms will be completed for all pregnancies reported during the study or in the 30 days after completion of the IMP. In addition, the Investigator will report to the Sponsor follow up information regarding the outcome of the pregnancy, including perinatal and neonatal outcome. Infants should be followed for 6 months.

If pregnancy is suspected while the subject is receiving IMP, the IMP will be withheld immediately until the result of the pregnancy test is known. If pregnancy is confirmed, the IMP will be permanently discontinued in an appropriate manner and the subject withdrawn from the trial. Protocol-required procedures for trial discontinuation and follow up will be performed unless contraindicated by the pregnancy.

If the Investigator becomes aware the female partner of a male subject becomes pregnant during the study or in the 30 days after the completion of IMP, consent will be requested from the female partner for collection of information on her pregnancy history and for information on the current pregnancy and birth.

# **7 GENERAL CONSIDERATIONS**

## **7.1 Basic Principles**

This research will be carried out in accordance with the protocol, the International Council for Harmonisation (ICH), Guideline for Good Clinical Practice: Consolidated Guidance (E6), and applicable regulatory requirements(s) including clinical research guidelines established by the Basic Principles defined in the U.S. 21 CFR Parts 50, 56, and 312 and the principles enunciated in the Declaration of Helsinki (revised version Fortaleza 2013).

## **7.2 Institutional Review Board**

This protocol will be reviewed by an appropriate IRB and study enrollment will not commence until the Board has approved the protocol or a modification thereof. The Board is constituted and operates in accordance with the principles and requirements described in 21 CFR Part 56.

## **7.3 Informed Consent**

Written informed consent will be obtained from each subject before performing any baseline study-specific evaluations. The informed consent document is prepared by the Investigator or designee, subject to review and approval by the Sponsor, and forwarded to a qualified IRB for final review and approval. The IRB-approved document must contain, at minimum, the eight basic elements of informed consent. Only the most

Protocol Pa-824-CL-011 V1.0

recently IRB-approved Informed Consent Document must be used to consent prospective study subjects. One copy of the signed and dated informed consent document will be given to the subject and the original retained by the Investigator/site.

#### **7.4 Indications for Subject Withdrawal**

Subjects will be free to withdraw at any time for any reason, or they may be withdrawn if necessary, to protect their health and safety or the integrity of the study data.

Subjects who are withdrawn from the study will not be replaced. Subjects in Panel 1 (fed) who do not complete the required FDA standard high-fat, high-calorie breakfast will be withdrawn from that study period.

The final report will include reasons for withdrawals. In the event of an early termination, subjects will undergo the procedures described in [Section 5.7](#).

#### **7.5 Termination of the Study**

The Principal Investigator reserves the right to terminate the study in the interest of subject safety and welfare. The Sponsor reserves the right to terminate the study at any time for administrative reasons.

#### **7.6 Documentation**

All documents pertaining to the study, including a copy of the approved protocol, copy of the informed consent document and Health Insurance Portability and Accountability Act (HIPAA) documents, completed CRFs (where applicable), drug accountability and retention records, and other study related documents will be retained in the permanent archives of the study site. These will be available for inspection at any time by the Sponsor or the FDA. Per 21 CFR 312, record retention for this study is required for a period of two years following the date on which this study agent is approved by the FDA for the marketing purposes that were the subject of this investigation; or, if no application is to be filed or if the application is not approved for such indication, until two years following the date on which the entire study is completed, terminated, or discontinued, and the FDA is notified.

Subject records will be kept private except when ordered by law. The following individuals will have access to study subject records: Principal Investigator and designees, study Sponsor, monitors, and auditors, the FDA, other government offices, and the IRB.

#### **7.7 Trial Monitoring**

Sponsor personnel (or designees) will be responsible for monitoring the study to ensure compliance with the protocol and GCP. Compliance may be verified by one or more of the following methods: on-site visits, frequent communication with the Investigator,

and/or review of CRFs and source documents. The Investigator agrees to permit such monitoring as well as audits or reviews by regulatory authorities and the IRB.

## **7.8 Reimbursement, Indemnity, and Insurance**

Reimbursement, indemnity, and insurance shall be addressed in a separate agreement on terms agreed upon by the parties.

# **8 PHARMACOKINETIC ANALYSIS**

## **8.1 Analytical Methodology**

Plasma samples will be analyzed for pretomanid using a validated assay. The samples from all evaluable subjects completing at least one study period will be analyzed. Samples from subjects who experience emesis within 4 hours of dosing will not be analyzed.

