**Criteria for evaluation:**

*Pharmacokinetics:*

Full pharmacokinetic profiles of pretomanid will be determined up to 96 hours after each intake of pretomanid. Blood samples for analysis of pretomanid concentrations will be drawn just before drug intake (pre-dose), and at 0.5, 1, 2, 3, 4, 6, 8, 12, 16, 24, 36, 48, 72, and 96 hours post dose (15 samples per dose).

Primary pharmacokinetic measures include  $T_{max}$ ,  $C_{max}$ ,  $AUC_{0-t}$ , and  $AUC_{0-inf}$ . Secondary pharmacokinetic measures include the ratio of  $AUC_{0-t}$  to  $AUC_{0-inf}$ ,  $T_{1/2}$ ,  $K_{el}$ ,  $Cl/F$  and  $Vd/F$ .

Statistical summaries for a given period will include data from all subjects for whom it was a completed period, even those who do not complete all four periods. The primary mixed-model analyses for relative bioavailability, dose, and food will use all the data from all completed periods.

Descriptive statistics will be used to summarize pretomanid plasma concentrations at each sampling time point and for derived plasma PK parameters, as applicable. Statistics include sample size (n), mean, SD, percentage coefficient of variation (% CV), geometric mean, median, minimum, and maximum.

All data will be listed, even if not used for statistical summaries or model-based analyses. But data that do not come from completed periods will be characterized in the listing as to their deficiency.

For each participant, pretomanid plasma concentration-time data will be graphically presented. Similarly, graphs of the mean plasma concentration-time profiles and overlay graphs with combined

Protocol Pa-824-CL-011 V.1.0

individual plasma concentration-time profiles will be produced. Additionally, pharmacokinetic parameters may be explored graphically.

The bioavailability of 4 x 50-mg dispersible tablets relative to the 200-mg reference tablet will be determined separately for each panel using a mixed model with the log transformed PK parameter ( $C_{max}$ ,  $AUC_{0-t}$ , and  $AUC_{0-inf}$ ) as response variable; sequence, period, and treatment as fixed effects; and participant as random effect.

The effect of dose on the relative bioavailability of the dispersible tablet will be determined separately for each panel using the same model as above.

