#### 6.1.3 Pharmacokinetic Analysis Set

All evaluable subjects completing at least one treatment period will be included in the PK analysis set.

QMD Ref: Worldwide-TMP-ST-006-4.0 Effective: 12Aug2019	Governing QMD: Worldwide-SOP-ST-001
Confidentiality Statement	

This document is the property of Worldwide Clinical Trials Inc. and may not be duplicated, copied, altered or removed from company without prior approval from Worldwide Quality Assurance or in compliance with Worldwide Standard Operating Procedures.

Worldwide Clinical Trials Controlled Quality Management Document		
 WORLDWIDE CLINICAL TRIALS	Sponsor: Protocol Number:	TB Alliance Pa-824-CL-011
STATISTICAL ANALYSIS PLAN – PHASE 1		

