#### **6.2.8.3 Emesis**

Subjects that experience emesis within 4 hours of dosing will be excluded from the PK analysis for the period during which the emesis occurred.

QMD Ref: Worldwide-TMP-ST-006-4.0 Effective: 12Aug2019	Governing QMD: Worldwide-SOP-ST-001
Confidentiality Statement	

This document is the property of Worldwide Clinical Trials Inc. and may not be duplicated, copied, altered or removed from company without prior approval from Worldwide Quality Assurance or in compliance with Worldwide Standard Operating Procedures.

Worldwide Clinical Trials Controlled Quality Management Document		
 WORLDWIDE CLINICAL TRIALS	Sponsor: Protocol Number:	TB Alliance Pa-824-CL-011
STATISTICAL ANALYSIS PLAN – PHASE 1		

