## 7 CHANGES TO PLANNED PROTOCOL ANALYSIS

No changes to the planned analyses have been identified.

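### Protocol 8.1 withholds emesis samples from assay by subject while SAP 6.2.8.3 excludes by period; read literally, three valid periods per affected subject go unassayed

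*Protocol*

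**What the plan says.** Protocol 8.1 (Analytical Methodology) sets out which samples are assayed. It gives an inclusion rule, "The samples from all evaluable subjects completing at least one study period will be analyzed", followed by the emesis rule, "Samples from subjects who experience emesis within 4 hours of dosing will not be analyzed". Both are written in terms of subjects, and the second names no period.

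SAP 6.2.8.3 (Emesis) uses the same 4-hour criterion but a different unit. Such subjects "will be excluded from the PK analysis for the period during which the emesis occurred".

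The other statements on which data are used also work by period:
- Protocol synopsis, Criteria for evaluation: "The primary mixed-model analyses for relative bioavailability, dose, and food will use all the data from all completed periods".
- SAP 6.1.3, in line with Protocol 8.2: "All evaluable subjects completing at least one treatment period will be included in the PK analysis set".

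SAP section 7 declares no departure from the protocol: "No changes to the planned analyses have been identified". The clarification-letter text in the protocol file and the SAP supplement do not touch section 8.1.

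**The concern.** The two emesis rules operate at different stages. Section 8.1 decides what is measured; the SAP decides what enters the analysis. If the laboratory follows 8.1 literally, a subject who vomits after one dose has no concentrations from any period. The SAP's narrower exclusion then cannot be carried out, because nothing is left to include.

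What would be lost is valid crossover data. The primary comparison is B against A within a panel. A subject who vomits after treatment C or D still has usable A and B periods under the SAP, but not under a literal 8.1. Withdrawn subjects are not replaced (Protocol sections 3 and 7.4), and the 24 per panel has no statistical derivation behind it (Protocol 5.1), so no planned allowance covers such losses. The event is foreseeable: Protocol 1.1 lists vomiting among the treatment-related adverse events.

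**Working it through.** **The wording**

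| Source | Unit of the rule | Stage |
|---|---|---|
| Protocol 8.1, emesis sentence | subject, no period named | assay |
| Protocol synopsis, mixed models | completed period | analysis |
| SAP 6.1.3, PK analysis set | subject with at least one completed period | analysis |
| SAP 6.2.8.3, emesis | period of the emesis | analysis |

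Protocol 7.4 is a useful comparison. For an unfinished breakfast in Panel 1 it limits the withdrawal to the study period concerned, and SAP 6.2.8.4 follows suit. The protocol therefore names the period where it means one, and 8.1 does not.

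**Inputs from the documents**
- 15 samples per period and 60 per subject (Protocol section 3).
- Two panels of 24 subjects, four periods each (Protocol 5.1 and synopsis).
- Emesis rate: not given.

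**The plan's own figure.** 15 x 4 = 60 samples per subject, as stated. The number of profiles is 48 x 4 = 192.

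**Loss for a subject with one emesis period**
- SAP rule: 15 samples lost, 60 - 15 = 45 kept (three periods).
- Protocol 8.1 read literally: 60 lost, of which 45 come from the three other periods.

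**Expected loss over both panels.** Assume emesis within 4 hours has probability p in each period, independently across a subject's periods.
- Period-level rule: 192 x p.
- Subject-level rule: 192 x (1 - (1 - p)^4).
- Subjects affected per panel: 24 x (1 - (1 - p)^4).

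| Assumed p | Profiles lost, SAP rule | Profiles lost, literal 8.1 | Ratio | Subjects affected per panel |
|---|---|---|---|---|
| 1% | 1.9 | 7.6 | 3.9 | 0.95 |
| 2% | 3.8 | 14.9 | 3.9 | 1.86 |
| 3% | 5.8 | 22.0 | 3.8 | 2.75 |

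**B/A pairs lost only because of the 8.1 wording.** These are subjects with emesis on C or D but not on A or B. With the same p for every treatment, the expected number per panel is 24 x (1 - p)^2 x (1 - (1 - p)^2):
- p = 1%: 24 x 0.9801 x 0.0199 = 0.47
- p = 2%: 24 x 0.9604 x 0.0396 = 0.91
- p = 3%: 24 x 0.9409 x 0.0591 = 1.33

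**Effect on the B/A interval.** In a complete panel of n subjects the residual degrees of freedom are 4n - 1 - (n - 1) - 3 - 3 = 3n - 6, which is 66 for n = 24. The width of the 90% interval on the log scale, relative to 24 retained pairs, is approximately sqrt(24/n) x t(0.95, 3n - 6) / t(0.95, 66):
- 1 pair lost (n = 23): 1.022
- 2 pairs lost (n = 22): 1.046
- 3 pairs lost (n = 21): 1.072

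**The case against.** The best defence is that 8.1 merely lacks a qualifier. It does not say that every sample or every period is withheld. Dosing happens four times, so its 4-hour clause could refer to the dose concerned. The SAP rule also starts from the subject before narrowing to the period, and the synopsis, Protocol 8.2 and the breakfast rule all point towards period-level handling. This makes the period-level intention likely. It does not make 8.1 say so, and 8.1 is the text that governs sample selection.

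Three stronger readings are tempting, and the documents do not support them.

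- A reader might infer that leaving the emesis period unassayed breaks the listing commitment, "All data will be listed, even if not used for statistical summaries or model-based analyses". It does not: a sample that is never assayed yields no concentration to list. Both documents keep that period out of the PK analysis, and SAP 6.2.8.3 does not require it to be assayed. Assaying it anyway would be a preference.
- A reader might infer that the other periods would be irretrievably lost. Appendix 1 splits each plasma sample into two aliquots, keeps samples frozen until assayed, and sends the frozen samples to the laboratory with no hold-back for emesis. Later assay may be possible. Nor do the documents show that the laboratory would apply the literal reading.
- A reader might infer that a study conclusion is at risk. The plan states no power target or equivalence limits that the loss would breach. If emesis clusters in the same subjects, fewer subjects are affected and the roughly fourfold ratio falls. If emesis occurs on A or B, the B/A pair is lost under either rule.

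**Conclusion.** Wrong as written: the emesis rules in Protocol 8.1 and SAP 6.2.8.3 differ in unit, and 8.1 taken literally also defeats the synopsis commitment to use all completed periods. The impact is minor to moderate.

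The per-subject consequence is a plain count and needs no assumed rate: 60 samples unassayed instead of 15 after one emesis period. The study-level size rests on an assumed 1-3% per period and on independence across periods: about 8-22 of 192 profiles instead of about 2-6. On the same assumptions, and with an equal rate for all treatments, the wording alone would cost roughly 0.5 to 1.3 B/A pairs per panel. If one to three pairs were lost in a panel, its B/A interval would be about 2-7% wider. With no emesis, nothing changes.

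**What to change.** Reword the emesis sentence in Protocol 8.1 so that only samples from the period in which emesis within 4 hours of dosing occurred are withheld, and state that the subject's other completed periods are assayed and analysed. This aligns 8.1 with SAP 6.2.8.3 and the synopsis; the SAP text needs no change.

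The cost is a one-sentence clarification, in the form the sponsor has already used for other sections, plus the assay of samples that are collected anyway. If samples have already been selected for assay, the study report should state which unit of exclusion the laboratory applied and whether any otherwise valid periods were left unassayed.

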## **8.2 Pharmacokinetic and Statistical Analyses**

Primary pharmacokinetic measures include  $T_{max}$ ,  $C_{max}$ ,  $AUC_{0-t}$ , and  $AUC_{0-inf}$ . Secondary pharmacokinetic measures include the ratio of  $AUC_{0-t}$  to  $AUC_{0-inf}$ ,  $T_{1/2}$ ,  $K_{el}$ ,  $Cl/F$  and  $V_d/F$ .

All evaluable subjects completing at least one treatment period will be included in the pharmacokinetic analysis.

Descriptive statistics will be used to summarize pretomanid plasma concentrations at each sampling time point and for derived plasma PK parameters, as applicable. Statistics include sample size (n), mean, SD, percentage coefficient of variation (%CV), geometric mean, median, minimum, and maximum.

For each participant, pretomanid plasma concentration-time data will be graphically presented. Similarly, graphs of the mean plasma concentration-time profiles and overlay graphs with combined individual plasma concentration-time profiles will be produced. Additionally, pharmacokinetic parameters may be explored graphically.

The bioavailability of 4 x 50 mg dispersible tablets relative to the 200-mg reference tablet will be determined separately for each panel using a mixed model with the log transformed PK parameter ( $C_{max}$ ,  $AUC_{0-t}$ , and  $AUC_{0-inf}$ ) as response variable; sequence, period, and treatment as fixed effects; and participant as random effect.

The effect of dose on the relative bioavailability of the dispersible tablet will be determined separately for each panel using the same model as above.

The effect of food on the relative bioavailability of pretomanid will be determined comparing, across panels, each formulation and dose taken after eating breakfast versus

Protocol Pa-824-CL-011 V1.0

the same formulation and dose taken in fasted conditions using a mixed model with the log transformed PK parameter as response variable; panel, sequence, period, treatment, and panel-by-treatment interaction as fixed effects; and participant as random effect.

The  $T_{max}$  of pretomanid for each of the formulations will be descriptively compared.

Other statistical models and/or population pharmacokinetic modelling may also be used for further data interpretation.

Pharmacokinetic calculations will be performed using appropriate software.

